Since inflammatory messengers such as TNF- α can stimulate osteoclasts without stimulating osteoblasts, long term elevation of TNF- α can cause osteoporosis. We will measure bone mineral density and will evaluate if the Z-scores are related to the inflammatory markers in particular to TNF- α . Such a finding would strengthen the development of a hypothesis of a possible relation, whereas its absence of such a relation would not necessarily negate this given the many parameters that can influence bone mineral density.

Finally, baseline pharmacokinetics of oral pharmacologic doses of taurine will be developed.

For safety reasons, the first two patients will be treated with a dose of 25 mg/kg/dose (maximum 1.5 g) twice daily. After review of safety parameters, the dose will then be increase to the planned dose of 75 mg/kg/dose (maximum 5 g) twice daily. The first four patients will be adults, before recruiting children in the study.

This short-term local pilot study will form the basis on which to later develop a national long-term study (orphan drug study), 4 years duration and placebo controlled, that will expand on the findings and include long-term variables such as those related to connective tissue and bone.

Primary Outcome Measure(s):

Oxidative stress and inflammation measures as follows:

- Luminex cytokine array studies to include the following cytokines
 - Interleukin 1-alpha (IL-1 α)
 - Interleukin 1-beta (IL-1 β)
 - Interleukin 1-ra (IL-1ra)
 - Interleukin 4 (IL-4)
 - Interleukin 8 (IL-8)
 - Interleukin 10 (IL-10)
 - TNF-alpha (TNF- α)
 - Monocyte Chemoattractant Protein-1 (MCP-1)
 - Interleukin 6 (IL-6)
 - Interleukin 12 (IL-12p70)
 - Interleukin 17 (IL-17)
 - MIP-1 α
 - MIP-1 β
- C-reactive protein (high sensitivity)
- Myeloperoxidase
- Transforming Growth Factor Beta (TGF- β)
- Extracellular superoxide dismutase
- TBARS
- ELISA Assay
 - Interleukin 1-alpha (IL α)
 - Interleukin 1-beta (IL- β)
 - Interleukin 10 (IL-10)
 - TNF-alpha (TNF- α)
- 8-Isoprostane metabolites (2,3-dinor-F₂-IsoPs combined signal) of 8-isoPGF_{2 α} , urine
- Dityrosine, urine
- Glutathione reduced (GSH) and oxidized (GSSG) in whole blood

Vascular coagulability markers:

- Endothelial Function as assessed by brachial artery flow-mediated dilation (FMD): percent change induced by hypoxemia in brachial artery diameter and flow measurement (derived from diameter and flow velocity)

- Platelet aggregation

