- 11-dehydro-thromboxane B2 (11-dehydro-TXB2) and 2,3-dinor-TXB2, urine

Bone mineral density by DEXA

B. Secondary Outcome Measure(s):

The relationship between the above noted oxidative stress markers and the related methionine cycle metabolites will be assessed

- Hcy
- Methionine
- Cystathionine
- Cysteine
- SAM (S-adenosylmethionine)
- SAH (S-adenosylhomocysteine)
- Dimethylglycine
- Betaine

Lipoprotein A will be assessed as confounding variable potentially modulating platelet aggregation and inflammatory response.

Molecular studies will be done given the known genotype/phenotype correlations in this disease and for verification of diagnosis.

Pharmacokinetic studies of taurine will be done for the first 12 hours following the first dose of taurine, and a steady state concentration will be obtained after 4 days of treatment.

C. Study Population Description:

Participants will be recruited from the Inherited Metabolic Diseases Clinic at Children's Hospital Colorado, The Children's Hospital of Philadelphia, and Duke University Hospital. Recruitment of patients being followed by other metabolic clinics may also be pursued if additional participants are needed. This will be done through their metabolic physician and / or through family support groups. Patients must meet all inclusion criteria. There will be no discrimination based on age, gender, or ethnic heritage.

D. Total Planned Number of Subjects:

- a. **For Single-Center Studies:** NA
- b. **For Multi-Center Studies – Up to 20**
 - i. **For this location: Up to 12**
 - ii. **For all locations: Up to 20**

Up to 16 patients will be exposed to taurine and analyzed. Allowing for 20 patients to sign consent is based upon the potential for patients who withdraw consent prior to drug exposure, may be potential screen failures, or fail to proceed to study after signing consent.

E. Inclusion Criteria:

Minimal inclusion criteria are:

1. A confirmed biochemical, molecular, or enzymatic diagnosis of classic homocystinuria due to cystathionine beta-synthase deficiency (OMIM 236200)
2. And not fully responsive to therapy (eg, tHcy levels above 50 $\mu\text{mol/L}$ on therapy including on B6 therapy)
3. Be over 8 years old and less than 50 years. The first four patients will be adults (age 18 – 50 years).
4. Be able and willing to provide informed consent

Exclusion Criteria:

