The above biomarkers and disease related metabolites will be also related to clinically relevant platelet function studies. We hypothesize that the inflammatory and oxidant environment pushes normal platelets into a chronic low-grade aggregation status, and that this improves with taurine. We will measure urinary 11-dehydroTXB2 and 2,3-dinor-TXB2 to reflect aggregation status, and in vitro platelet aggregation studies to reflect the platelet function. The metabolites 11-dehydroTXB2 and 2,3-dinor-TXB2 have been reported as elevated in CBSDH patients.

Following the observational studies, participants will be treated with oral taurine 75 mg/kg (maximum 5 grams) BID for 4 ½ days. The first two patients will be treated with a dose of 25 mg/kg (maximum 1.5 g) twice daily, before increasing the dose to the full study dose. USP grade taurine supplied by Solace Nutrition, lot number 6608 (Solace Nutrition, [name]) and Medisca Inc, lot number 105927 (Medisca Inc, [name]) will be used. If for any reason this lot number changes, we will submit additional Certificate of Analysis to the FDA and COMIRB for the new lot numbers. Participants will be weighted on visit day one. Based on the patient weight, a prescription order will be written by the MD Co-investigator or CTRC nurse practitioner for taurine and will be given to The Children's Hospital Pharmacy Investigational Drug Services. Individual, single dose packets will be weighed and dispensed by the pharmacy to the Clinical and Translational Research Center (CTRC). Each single dose packet will be labeled with the study medication name and dose. The amount of product needed for the first 4 days of the study period will be dispensed up front in a container that is labeled with subject's name, medication name, medication dose, and directions for administration. Based on the prescription order, the Children's Hospital Pharmacy will dispense the medication to the inpatient Clinical and Translation Research Center (CTRC). The first dose of study medication will be administered orally to the study patient by a RN. The RN will mix taurine with 150mls of water or the individual's favorite juice. The RN

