It is anticipated that the biomarkers of oxidative stress and inflammation will be increased above the norm in participants and the degree of elevation will be related to Hcy levels. A decrease in the elevation of the biomarkers is anticipated following treatment with taurine. It is also anticipated that FMD studies will be abnormal in participants and that improvement will be seen following taurine supplementation. We anticipate that platelet aggregation studies will be normal, but that markers of generalized activation of platelets, thromboxane B2 metabolites, are elevated, and will reduce with treatment. Bone mineral density Z-scores will be related to baseline TNF- α levels.

J. Potential Problems:

1. Recruitment: Given the rarity of the disorder, our potential participant sample volume is low. Geographic and economic issues may make it difficult for some

potential subjects to participate in the study. Low participation in the study might impact the statistical analysis of data. Should insufficient patients be recruited locally, then advertisement through national organization will be done to increase participation. Of note, while there is one report of Vitamin C supplementation ameliorating endothelial dysfunction in individuals with CBSDH, its use has not been widely investigated and use of Vitamin C to treat homocystinuria is not standard of care. We therefore do not anticipate this excluding criteria to markedly effect recruitment.

Patients with prescribed salicylate (such as Aspirin) therapy will not have this discontinued but will be excluded from the platelet function studies. We anticipate that this will impact up to 25% of the recruited population. A recruitment of 12 patients will likely provide a minimum of 8 patients in which this clinically relevant measure can be analyzed. Should the percentage of patients taking platelet aggregation inhibitors exceed our anticipated number, then we will plan to extend the study to increase the number of patients to be enrolled. Similar considerations are for use of cGMP phosphodiesterase 5 inhibitors (such as Viagra) and exclusion of FMD studies, although we doubt that the rate of patients taking this medication in our young age group would be as high as 25%. Overall, our goal is to recruit 8 patients that participate in all aspects of the study and are treated at the target dose of 150 mg/kg/day (maximum 10 g/day).

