For TBARS, conventionally treated CBSDH patients had a mean TBARS of 2.92 ± 0.38 nmols/ml compared with mean TBARS of 2.23 ± 0.33 nmols/ml in controls. When the sample size is 8, a single group t-test with a 0.05 two-sided significance level will have 99% power to detect the difference between a null hypothesis mean TBARS of 2.23 nmols/ml and an alternative mean of 2.92, assuming that the standard deviation is 0.38 nmols/ml.

Analysis plan: The mean, median, standard deviation, and 95% confidence intervals for TNF- α and TBARS will be generated.

B. Does taurine decrease the primary outcome biomarkers of TNF- α and TBARS?

Sample size and statistical power consideration: We hypothesize that taurine treatment will decrease oxidative stress and inflammation in CBSDH patients, which will be evaluated by comparing the levels of TBARS and TNF- α after 4 hours and 4 days on taurine compared to the corresponding baseline levels (before treatment). The minimum number of evaluable patients on high dose taurine therapy is eight, but can be as high as 10. Eight evaluable baseline paired samples provide 80% or higher power to detect an effect size in the range of 1.2-1.5, which is the standardized (by the standard deviation of the changes) mean difference between the alternative hypothesis of reduced oxidative stress/inflammation due to taurine therapy and the null hypothesis of high oxidative stress/inflammation before taurine treatment. A paired t-test was used for the calculation with a one-sided significance level of 0.05.

Power	Effect Size
0.95	1.30
0.9	1.15
0.8	0.98

To translate the effect size into the actual detectable level of the two markers, preliminary data showed a mean baseline TNF- α of 19.33 ± 5.56 pg/ml in treated CBSDH patients. Assume the correlation coefficient (Rho) of TNF- α between baseline and 4 days (or 4 hours) on taurine therapy is in the typical range of 0.1-0.5, and the variance of TNF- α on four days (or 4 hours) at taurine therapy time points are the same as at the baseline, then the detectable mean value of TNF- α at 4 days (or 4 hours) on therapy is 12.0 (for Rho=0.1)-13.9 (for Rho=0.5) with 80% power. Similarly, mean baseline TBARS of 2.92 ± 0.38 nmols/ml were observed in CBSDH (treated) patients, assume that taurine can reduce TBARS level, the detectable mean value of TBARS at 4 days (or 4 hours) on therapy is 2.42 (for Rho=0.1)-2.55 (for Rho=0.5) with 80% power.

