Analysis plan: The mean and standard deviation of TNF- α and TBARS at baselines and on therapy will be calculated, and the changes from baseline to therapy times will also be calculated and reported along with 95% confidence intervals. One-sample t-test will be used to test if the changes are significantly different from zero for both TNF- α and TBARS.

II. Secondary outcome measures: exploratory studies of other biomarkers of oxidative stress and inflammation, relationship to metabolites and to markers relevant of symptomatology

- A. Other biomarkers of oxidative stress and inflammation: A similar analysis as outlined above for TNF- α and TBARS will be done for the exploratory biomarkers of oxidative stress and inflammation. Because of the multiple comparisons in the many biomarkers, an adjustment of p-values will be done (such a Bonferroni or given the exploratory nature, a more relaxed method such as a family wise approach (false discovery rate) may be used). The findings will be used to generate new hypotheses for further study on independent datasets.
- B. Relationship to metabolites: For the relation to metabolites, the biomarkers listed in Table 1 will be correlated with total Hcy concentration using a Spearman's rank correlation coefficient, since the Hcy values are not likely to be normally distributed.
- C. Relationship to pathophysiologically relevant parameters of major symptomatology: For the evaluation of endothelial function abnormalities in CBSDH patients and its mitigation with taurine supplementation, the percent change in brachial artery diameter and the percent change in brachial artery flow induced by hypoxemia, will be compared between pre-treatment and after 4 days treatment. A paired t-test will be calculated to test if the percent change is significantly different from zero. To test whether platelet aggregation is mitigated by taurine supplementation, percent aggregation will be compared pre-treatment and at day 4 post-treatment using a paired t-test. Also, urine levels of thromboxane B2 metabolites will be similarly compared. To relate the bone mineral density to TNF- α levels, the Z-score of the BMD will be related to pre-treatment TNF- α levels and the correlation assessed using a Spearman or a Pearson product moment correlation coefficient, depending on the evaluation of normality of distribution.

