Special Care Clinic
[name]
[name]

[name]
[contact]
[name]

[name] (alternate)
[contact]
[name]

Unanticipated problem or events, especially problems or events that are possibly or probably related to the study or research procedures will also be looked for. This includes monitoring for serious adverse events (SAEs) since such an event is not anticipated. In an event of an SAE, the monitoring PI will discuss the event with one of the co-investigator MDs within 24 hours of knowledge of the event to allow for decisions regarding the data and the safety to all participants. All unanticipated problems and unanticipated events will also be discussed with one of the co-investigating MDs within five working days of knowledge of the problem or event. Any identified trend in AEs will also be discussed within five working days of knowledge of the trend with one of the co-investigator MDs. Of note, the minimal risk for adverse events relative to taurine intake, the low number of participants (N=16 with drug exposure) and short duration of the study (5 days) make it very unlikely that any AE trend would be detected much before the end of the study.

There are no conflicts of interest for the PI or the co-investigator MDs responsible for data safety management.

B. Describe SAEs and AEs for this protocol and the SAE/AE reporting plan:

Events that result in death, immediate hospitalization, or prolonged hospitalization to prevent death or serious disability will be considered SAEs. Any other untoward medical occurrence temporally associated with the study will be considered AE. This includes headaches, gastrointestinal discomfort, and other events captured on the adverse event/compliance sheet that are without significant health risk and/or are potentially unrelated to study. Clinically significant changes in blood pressure or safety monitoring labs will be considered an AE. Specifically, liver function results that exceed two times the upper limit of normal, triglycerides greater than 400 mg/dl, and/or hypotension, with a blood pressure <90mmHg in adults or <the 5th percentile for age in children after taurine supplementation, will

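### Do the limit of 10 high-dose patients and the silence about the two low-dose patients undermine the change-from-baseline tests?

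*Combined protocol and SAP*

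**What the plan says.** Section 5.K, part I.B, sizes the change-from-baseline comparison of TNF-α and TBARS on patients at the full study dose: "The minimum number of evaluable patients on high dose taurine therapy is eight, but can be as high as 10". The power statement uses the lower figure: "Eight evaluable baseline paired samples provide 80% or higher power". The analysis plan closing part I.B says "One-sample t-test will be used to test if the changes are significantly different from zero" for both markers. It names no analysis set, sets no dose restriction, and does not say whether the test is one- or two-sided.

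The total is given elsewhere. Section 5.D: "Up to 16 patients will be exposed to taurine and analyzed". Section 8.A, on why a trend in adverse events is unlikely to show early, cites "the low number of participants (N=16 with drug exposure) and short duration of the study (5 days").

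The lower starting dose is described in Section 5.A ("the first two patients will be treated with a dose of 25 mg/kg/dose") and in Section 5.G ("The first two patients will be treated with a dose of 25 mg/kg (maximum 1.5 g) twice daily, before increasing the dose"). Section 5.J.1, on the platelet measure, says "A recruitment of 12 patients will likely provide a minimum of 8 patients in which this clinically relevant measure can be analyzed". The same section sets the overall goal as 8 patients who complete every part of the study at the target dose.

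**The concern.** Two things look wrong.

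The first is the count. With up to 16 exposed and two on the lower dose, up to 14 can be at the target dose, yet part I.B stops at 10. A wrong patient number in a sample-size section raises the question of whether the power was worked out for a different study.

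The second is the analysis set. Power is computed for high-dose patients, but the test is described only as a test of the changes. Section 5.D says that all exposed patients will be analysed, which could be read as including the two low-dose patients in the primary tests. The study has one arm and may have as few as 8 target-dose patients, so two more on about a third of the dose could move the mean change. If the choice were left until the results were known, it could be made to suit them. The same silence extends to the pre/post comparisons in part II of Section 5.K. The baseline comparison with controls (part I.A) does not depend on dose and is unaffected.

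**Working it through.** **Inputs.** Exposed: 16 (Sections 5.D and 8.A). Low-dose: 2 (Sections 5.A and 5.G). Minimum at the high dose: 8; stated maximum: 10; paired t-test, one-sided 0.05 (Section 5.K, part I.B). Baseline TNF-α 19.33, SD 5.56; TBARS 2.92, SD 0.38; correlation 0.1 to 0.5 (same place).

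**1. The plan's own figures.** Power for a paired t-test comes from the noncentral t distribution with n − 1 degrees of freedom and noncentrality d√n. With n = 8 and one-sided 0.05:

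| Power | Effect size in plan | Recomputed |
|---|---|---|
| 0.95 | 1.30 | 1.299 |
| 0.90 | 1.15 | 1.153 |
| 0.80 | 0.98 | 0.978 |

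Detectable mean at 80% power = baseline − 0.98 × SD × √(2(1 − ρ)).

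- TNF-α, ρ = 0.1: SD of change = 5.56 × √1.8 = 7.46; 19.33 − 7.31 = 12.02 (plan: 12.0).
- TNF-α, ρ = 0.5: SD of change = 5.56; 19.33 − 5.45 = 13.88 (plan: 13.9).
- TBARS: 2.42 and 2.55, as in the plan.

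All of these rest on n = 8. The range of 1.2 to 1.5 in the text above the table does not match the one-sided table. It is close to the two-sided results at n = 8 (1.16 at 80% power, 1.50 at 95%). That is a separate matter and does not involve the count of 10.

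**2. The count.** 16 − 2 = 14, against the stated 10. The number 10 equals 12 − 2, and 12 appears in Section 5.J.1 and as the lead-site limit in Section 5.D, but the documents do not say where 10 came from. Power at d = 0.98, one-sided, is 0.80 for n = 8, 0.89 for n = 10 and 0.97 for n = 14. A higher maximum could only add to the power claimed.

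**3. Pooling the two low-dose patients.** Let f be the low-dose effect as a fraction of the target-dose effect. The documents give no value, so f is an assumption, taken over its range from 0 to 1. The SD of the change is set to 1, with a shift of 0.98 at the target dose and 0.98f in two patients. Pooled power is by simulation.

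| Set | f = 0 | f = 1/3 | f = 1 | Target dose alone |
|---|---|---|---|---|
| 8 + 2, one-sided 0.05 | 0.69 | 0.78 | 0.89 | 0.80 |
| 14 + 2, one-sided 0.05 | 0.94 | 0.96 | 0.98 | 0.97 |
| 8 + 2, two-sided 0.05 | 0.54 | 0.64 | 0.79 | 0.66 |

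The two-sided row is there because the analysis plan does not state sidedness. For the one-sided test, pooling breaks even at f of about 0.44 (8 + 2) to 0.48 (14 + 2): below that it lowers power, above it raises power.

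The mean change shrinks by 1 − (n + 2f)/(n + 2), where n is the number at the target dose. For 8 + 2 this is 20% at f = 0, 13.3% at f = 1/3 and 0% at f = 1. For 14 + 2 it is 12.5%, 8.3% and 0%. On a TNF-α change of 5.45 to 7.31 pg/ml with 8 + 2, the loss at f = 1/3 is 0.73 to 0.97 pg/ml.

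The value f = 1/3 matches the dose ratio 25/75. The caps make that ratio 1.5/5 = 0.30 for patients of 5,000/75 = 66.7 kg or more.

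**The case for a change.** The strongest case for a change concerns the analysis set. TNF-α and TBARS are the named primary efficacy parameters, the study has a single arm, and no section describes blinding. Section 5.D's statement that exposed patients will be analysed points towards pooling; the power basis points towards target dose only. No sentence settles it. At the minimum size the choice moves power between 0.69 and 0.89, and one sentence would close the gap. On the count, no allowance for losses from 14 to 10 is stated: the margin from 20 consenting to 16 exposed covers losses before treatment.

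Much of this stands as fact. The 10 does not fit the 16, and the set is not named in the analysis plan. What does not follow is that the plan would give a wrong answer. The test is described under the same heading as the power statement, where the only population named is patients on the high dose, and Section 5.J.1 sets its goal at 8 patients at the target dose. Section 5.D's sentence explains how many consents are needed to reach 16 treated patients; it does not define a set for a particular test. The figures 0.69 and 0.89 are the two ends of an assumption, and they lie on opposite sides of 0.80.

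Nor is the 12 in Section 5.J.1 a rival total. It illustrates how many recruits would leave at least 8 for the platelet measure after exclusions for salicylate use, and the same paragraph allows enrolment to be extended. Sections 5.D and 8.A already agree on 16.

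**Conclusion.** No change follows. The upper limit of 10 is a clerical slip: it should be compatible with 16 exposed less 2, or 14, but no power or detectable-level figure uses it. That it is left over from a planned total of 12 is a plausible inference, not something the documents state.

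The unnamed analysis set is a gap that an analyst would fill sensibly, by testing the target-dose patients for whom the power was computed and showing the two low-dose patients separately. If they were pooled instead, the effect has no determined sign. At the minimum size (8 + 2, effect size 0.98, one-sided 0.05), power would be 0.69 to 0.89 against 0.80, and 0.78 if effect is proportional to dose. With 14 + 2 it would be 0.94 to 0.98 against 0.97. These figures assume normal changes with the same SD at both doses, and a low-dose effect between none and all of the target-dose effect. If the test is two-sided, the 8 + 2 range is 0.54 to 0.79 against 0.66, and the direction again depends on the assumed effect. For a pilot that plans on 8 target-dose patients, this does not alter the design, the sample-size justification or the reading of the primary tests.

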For these latter two groups of patients, the standard treatment is a methionine (hence natural protein) restricted diet and supplementation with betaine (trimethylglycine) which serves as a methyl donor for the remethylation of Hcy to methionine catalyzed by betaine-homocysteine methyltransferase in the liver. Although methionine restriction and betaine supplementation have been successful in terms of improving clinical outcome, limitations and adverse side effects exist. Methionine restriction adversely impacts quality of life and is often associated with poor compliance. Patients diagnosed after the infantile period are very rarely able to sufficiently comply with its severe restrictions and special products. Betaine treatment in isolation often does not sufficiently lower plasma Hcy levels and can exacerbate already elevated methionine levels with a risk of cerebral edema. Illustrating the above, this clinic follows seven patients with B6 non-responsive CBSDH. All require diet therapy, as betaine therapy in isolation is not sufficient. Only one of the seven individuals is able to adhere to the dietary recommendation required to achieve a reduction in Hcy levels to a range that is therapeutic ($< 50 \mu\text{M}$ total homocysteine, but still well elevated above normal which is $2\text{-}12 \mu\text{M}$). Consequently, there is currently a need for novel therapeutic strategies for CBSDH. To date, the rational design of such strategies has been hampered by the lack of understanding of the underlying pathophysiological mechanisms involved in the disease leading to the thromboembolic events. Similarly, there is currently no knowledge about the mechanism of the skeletal and connective tissue defects in this condition. Symptoms of lens detachment, arachnoid status, and osteoporosis have persisted even in treated patients, and will require a new approach.

While no single mechanism has been satisfactorily defined in CBSDH-related thromboembolic events, a body of data has accumulated implicating oxidative stress.

General evidence:

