Taken together, these observations indicate that dietary supplementation with taurine has significant therapeutic potential for treating CBSDH in humans. With its low-cost and low risk of side-effects, we propose investigation of taurine as an adjuvant therapy for betaine supplementation and methionine restriction.

Preliminary data from human CBSDH patients poorly compliant with standard therapy showed elevations of TNF- α (39.36 ± 4.85 pg/ml in un- or poorly treated and 19.33 ± 5.56 pg/ml in treated patients, versus controls 1.89 ± 0.53 pg/ml, $N = 10$, $p < 0.0001$) and TBARS (4.08 ± 0.56 nmol/ml in un- or poorly treated and 2.92 ± 0.38 treated patients, versus controls 2.23 ± 0.33 nmols/ml, $N = 10$, $p < 0.0001$ and < 0.0027 respectively). Cytokine profiling confirmed significant elevations in TNF- α , and the inflammatory cytokines IL-1 α and IL-1 β . Study subjects provided informed written consent for COMIRB protocol number 00-359.

5. Research Design and Methods

A. Overview - Brief Summary of Study Rationale:

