Patients taking platelet aggregation inhibitors such as salicylate on a PRN basis that are unwilling or unable to stop taking the medication for the study period to include the two week washout period will be excluded from the study for the impact on platelet function but will participate in the remainder of the study

2. Normal values: Normal values are available for nearly all measurements. Normal values are being developed by the CTRC laboratory for the Luminex panel of inflammatory markers and for TGF-beta.. Normal values for FMD studies will be developed from patients previously analyzed in the adult CTRC using the same methodology as discussed with [name].

K. Statistical Sampling, Sample Size and Analytical Plan

This study benefits from the statistical assistance provided through the CCTSI. The protocol was reviewed by biostatistician [name]. The services of [name] will be retained through the study.

I. The primary efficacy outcome parameters (Aim 2) are TBARS and TNF- α . For each of these two parameters, there are two questions:

- A. Is the biomarker elevated in the untreated patient compared to control?
This question is required to validate the preliminary data.
- B. Does the biomarker decrease following treatment with taurine, after 4 hours treatment (immediate response) and after 4 days of treatment (short term treatment)?
This question evaluates the impact or treatment on the primary outcome markers

Sample size and statistical power consideration:

A. Is the biomarker (TNF- α , TBARS) elevated in CBSDH patients? Hypothesis 1 states that extracellular biomarkers of oxidative stress and inflammation in CBSDH patients will be increased compared with control patient values. The proposed study will include mostly patients who are untreated or poorly treated (non-compliant patients) for conventional

treatment, but can also have treated patients. To be conservative, we will use the preliminary data from the treated patients to power the study.

For TNF- α , preliminary data showed a mean of 19.33 ± 5.56 pg/ml in CBSDH conventionally treated patients compared with a mean in controls of 1.89 ± 0.53 pg/ml. When the sample size is 8, a single group t-test with a 0.05 two-sided significance level will have 99% power to detect the difference between a null hypothesis mean TNF- α of 1.89 pg/ml and an alternative mean of 19.33, assuming that the standard deviation is 5.56 pg/ml.

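### Does using treated-patient TBARS data make Part B's detectable drop too optimistic for a mostly poorly treated cohort?

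*Combined protocol and SAP*

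**What the plan says.** Section 5.K.I.B (taurine effect) plans a one-sided paired t-test at 0.05. On numbers it says: "The minimum number of evaluable patients on high dose taurine therapy is eight, but can be as high as 10". Power is tabulated against a standardized effect, the mean change divided by the SD of the changes: 0.98, 1.15 and 1.30 for 80%, 90% and 95%. The section then converts the 80% entry to measured units. For TBARS the input is treated patients ("mean baseline TBARS of 2.92 ± 0.38 nmols/ml were observed in CBSDH (treated) patients"), and "the detectable mean value of TBARS at 4 days (or 4 hours) on therapy is 2.42" for a correlation of 0.1, rising to 2.55 for a correlation of 0.5.

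Section 4 (Preliminary Studies) gives both groups: 4.08 ± 0.56 "nmol/ml in un- or poorly treated and 2.92 ± 0.38 treated patients".

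Section 5.K.I.A describes the expected cohort: "The proposed study will include mostly patients who are untreated or poorly treated (non-compliant patients"), "but can also have treated patients. To be conservative, we will use the preliminary data from the treated patients to power the study".

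Two other places bear on the mix. Section 3 says of the lead clinic's B6 non-responsive patients: "Only one of the seven individuals is able to adhere to the dietary recommendation required to achieve a reduction in Hcy levels". The second inclusion criterion (section 5.E) asks for patients "not fully responsive to therapy (eg, tHcy levels above 50" µmol/L on therapy.

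**The concern.** The cohort described in Part A and the SD used in Part B do not match. The un- or poorly treated group, expected to be the majority, has a TBARS SD 47% larger than the treated group (0.56/0.38 = 1.47). In a paired design the detectable absolute drop is proportional to the SD of the change, so a larger SD means a larger detectable drop.

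The reason given for using treated data also does not carry over fully. In Part A the treated patients lie closer to controls, so using them is cautious. In Part B the comparison is within patient, and for an absolute TBARS drop the smaller SD is the favourable choice.

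TBARS is one of the two primary efficacy markers, and 2.42-2.55 is its only sensitivity statement in nmol/ml. A reader could believe the study has 80% power for a drop of 0.37-0.50 in the patients it will enrol when the true figure is lower.

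**Working it through.** **Inputs.** From 5.K.I.B: n = 8 (up to 10), one-sided 0.05, paired t-test, rho 0.1-0.5, equal variance before and on therapy. From section 4: treated 2.92 ± 0.38, un- or poorly treated 4.08 ± 0.56, controls mean 2.23. The ± is read as an SD, as the protocol itself does.

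**Formulas.** SD of change = SD × √(2(1 − rho)). Detectable drop = effect size × SD of change. Power comes from the noncentral t distribution with n − 1 degrees of freedom.

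**1. The plan's own figures.** For n = 8 the effect sizes are 0.978, 1.153 and 1.299 for 80%, 90% and 95% power, which agree with the table.
- rho 0.1: 0.38 × √1.8 = 0.510; 0.98 × 0.510 = 0.50; 2.92 − 0.50 = 2.42.
- rho 0.5: 0.38 × √1 = 0.380; 0.98 × 0.380 = 0.37; 2.92 − 0.37 = 2.55.

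Both reproduce.

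**2. All eight un- or poorly treated.**
- rho 0.1: 0.56 × √1.8 = 0.751; 0.98 × 0.751 = 0.74; mean 3.34.
- rho 0.5: 0.56 × √1 = 0.560; 0.98 × 0.560 = 0.55; mean 3.53.

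**3. A mix.** The protocol says only that such patients will be the majority; 5-7 of 8 is an assumption. With rho applied within each group and a similar drop in both, the difference in baseline means cancels in the paired change. The pooled SD is √[(k × 0.56² + (8 − k) × 0.38²)/8]. Power is for the plan's own drop (0.37 at rho 0.5, 0.50 at rho 0.1), applied equally to every patient.

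| k of 8 un- or poorly treated | Pooled SD | Detectable drop, rho 0.5 to 0.1 | Power for 0.37 / 0.50 |
|---|---|---|---|
| 5 | 0.500 | 0.49-0.66 | 60% / 60% |
| 6 | 0.521 | 0.51-0.69 | 57% / 57% |
| 7 | 0.541 | 0.53-0.71 | 54% / 55% |
| 8 | 0.560 | 0.55-0.74 | 52% / 52% |

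Simulation with unequal group SDs agrees to within about one percentage point.

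**4. Dependence on the effect scale.** The last column assumes the same absolute drop in both groups. Two other scales are at least as natural.
- *Equal percentage fall.* The coefficients of variation are 0.38/2.92 = 13.0% and 0.56/4.08 = 13.7%. The detectable fall is 12.8-17.1% of baseline in treated patients and 13.5-18.0% in un- or poorly treated patients. Power for the percentage fall implied by 0.37/2.92 or 0.50/2.92 is about 76% for 5-8 of 8.
- *Equal fraction of the elevation over controls.* The excess is 2.92 − 2.23 = 0.69 in treated patients and 4.08 − 2.23 = 1.85 in un- or poorly treated patients. A drop of 0.37 is 0.37/0.69 = 54% of the treated excess. The same fraction of 1.85 is 0.99, against an SD of change of 0.56 at rho 0.5. Power is about 98% or more for 5-8 of 8.

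**5. The other primary marker.** For TNF-α the order of the SDs reverses (treated 5.56, un- or poorly treated 4.85). The detectable drop is 5.45-7.31 with treated data and 4.75-6.38 with un- or poorly treated data, so there the treated input is the cautious one.

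**6. How firm 0.56 is.** Section 4 gives N = 10 without a clear split by group. If there were 10 per group, the 95% intervals for the SDs would be 0.39-1.02 and 0.26-0.69, with a variance-ratio p of 0.26; with 5 per group p would be 0.47. The data do not establish that the two SDs differ.

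**The case for a change.** The strongest case for a change runs as follows. The mismatch is in the protocol's own text, and the stated reason for the treated input does not hold on the scale that Part B reports. The smaller of two equally uncertain SDs was used without a reason that fits a within-patient comparison. Even a 50% mix gives a detectable drop of 0.47-0.63 and about 63% power for 0.37-0.50. Pooling within groups is also the lenient reading: applying the plan's formula to the total SD, including the spread between groups, would give 0.65-0.99. The study is meant to support a later long-term trial, and a second scenario would cost only a few sentences.

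The arithmetic and the point about the word conservative both stand. The treated input is the favourable one for an absolute TBARS drop, and a reader who carries that word from Part A into Part B would be misled on this item.

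The rest does not reach a needed change. The figure is right for the group it names, that group is named in the sentence, and the SD for the other group is printed in section 4. The drop of 0.37-0.50 is the smallest one detectable at 80% power, not a declared target. The protocol's hypothesis in section 2 and its Expected Results speak of reducing an elevation, and on that scale the treated input is conservative. The total-SD reading counts a baseline difference between groups that cancels in the paired change when the drops are similar.

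**Conclusion.** No change is needed. Part B's power rests on the standardized effect-size table, which is correct for n = 8 and independent of either TBARS SD. The conversion to 2.42-2.55 is an illustration, correct and labelled as the treated case.

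For the expected cohort the absolute detectable drop would be larger: 0.49-0.71 nmol/ml with five to seven of eight un- or poorly treated, 0.55-0.74 with all eight, against 0.37-0.50 as stated. This rests on an assumed mix, on rho of 0.1-0.5 within groups, and on an SD of 0.56 from a small sample that cannot be told apart from 0.38. The fall in power to about 54-60% for five to seven of eight needs the further condition of the same absolute drop in every patient. Without it, power is about 76% (equal percentage fall) or about 98% and above (equal fraction of the elevation).

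A second scenario would alter no sample size, test or table entry. The analysis plan in 5.K.I.B already commits to reporting changes from baseline with 95% confidence intervals, so the precision actually reached, including that of a null result, will be visible from the data. In a pilot limited by the rarity of the disease, that is enough.
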